Anaphylactic and anaphylactoid reactions have been reported. Pruritus, rashes and urticaria may occur with a frequency of 0.1% to 1% but progression to anaphylactoid shock (angioedema, bronchospasm) occurs only in isolated cases. Erythema (reddening of the skin) has been reported at an unknown frequency.

Miscellaneous

Rarely, the following were reported: brittle fingernails, blurred vision, conjunctivitis, earache, scotoma, bad taste in the mouth, excessive salivation, malaise, sore throat, swollen neck glands, weight change.

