6.7 Adverse Event Reporting

Weekly research meeting will be held by investigators to review the study progress and adverse events. Adverse events will be handled according to the guidelines published in: "*Safety monitoring and reporting in clinical trials involving therapeutic goods.(2016) Canberra: National Health and Medical Research Council*".

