8.2 Statistical Analysis Plan

This is a pilot study aiming to evaluate the feasibility of a full-scale project as such we will assess the following:

- 1) Exclusion/enrolment rates
- 2) Withdrawal rate
- 3) Tolerance to trial medication
- 4) Compliance to therapy
- 5) Data integrity
- 6) Protocol violations and trial completion rate
- 7) Dilatations required
- 8) Adverse Events

Treatment efficacy will be evaluated however the goal is to estimate the trajectory of change of the two continuous outcome variables (SSQ and Pharyngeal Compliance) within subjects from immediately post-dilatation out to 12months. These estimates will help to determine required sample size to show clinically relevant effect and design a full-sized trial competitive for Cat 1 funding.

Outcome measures

Primary: Dysphagia symptom severity - assessed by SSQ (see above) at baseline before dilatation and every 3 months.

Secondary: Pharyngeal compliance assessed by EndoFLIP at 12 months (see above);

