10.2 Follow up phone interview

At monthly intervals from time of dilatation to 3 months (total 2 phone calls, the first at 4 weeks following enrolment and then at 8 weeks post enrolment.)

The researcher will greet and introduce themselves to participant.

The researcher will explain the purpose of phone call, to assess how the participant is tolerating medication on post dilatation for stricture trial. The researcher will inform the patient that that notes will be taken during the phone call to ensure that there is an accurate record of any issues or concerns raised.

Researcher will ask patient

- i. If they have experienced any side effects from medication?
- ii. If they have experienced any unexpected or severe bleeding for example prolonged nose bleed, or prolonged bleeding from relatively minor injury.
- iii. If they have been able to comply with dosing as prescribed
- iv. If they have commenced any new medication or supplement since the last contact
- v. If they have any concerns with continuing on the trial
- vi. If they have any feedback regarding the medication or trial that they would like us to consider

The researcher will then check that the patient has adequate numbers of medication.

Finally, the researcher will confirm the date and time of the next phone consult. At the 8 week phone call the researcher will confirm the date for the 12 week visit. Which can either be done at the Swallowing Clinic, a Cancer Care Centre follow up appointment or if they are referred from an external centre (or by patient choice) the SSQ can be posted with an addressed return envelope.

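### Apart from bleeding, the phone script asks only for side effects the patient attributes to the medication, so other adverse events may be under-ascertained

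*Protocol*

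**What the plan says.** Section 10.2 of the Protocol fixes the telephone script, used at 4 and 8 weeks after enrolment. It has six items, and the researcher takes notes of whatever is raised. The call is introduced to the patient as a check on how the medication is being tolerated.

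- Item i, on harms in general: "If they have experienced any side effects from medication".
- Item ii, on bleeding: "If they have experienced any unexpected or severe bleeding for example prolonged nose bleed, or prolonged bleeding from relatively minor injury".
- Item iii asks about adherence to dosing.
- Item iv: "If they have commenced any new medication or supplement since the last contact".
- Item v: "If they have any concerns with continuing on the trial".
- Item vi: "If they have any feedback regarding the medication or trial that they would like us to consider".

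Section 8.2 lists eight things the pilot will assess. Item 3 is "Tolerance to trial medication" and item 8 is adverse events; they are separate entries. Section 6.7 states: "Weekly research meeting will be held by investigators to review the study progress and adverse events". It refers the handling of adverse events to a national guideline. Section 6.8 covers all serious adverse events as that guideline defines them.

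**The concern.** An adverse event is normally recorded whatever its cause, and relatedness is judged afterwards. Item i reverses that order: patients must decide that the tablets caused a problem before the question applies to it.

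This population has ready alternative explanations. Participants have had radiotherapy, have dysphagia and have just been dilated. Section 6.4.2 lists among rarely reported pentoxifylline effects "bad taste in the mouth, excessive salivation, malaise, sore throat, swollen neck glands, weight change", and a head and neck cancer survivor could easily put several of these down to past treatment or the procedure. An intercurrent illness or an admission for another reason also falls outside the question.

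What is at stake is the absolute adverse-event rate, which the pilot is meant to report and which will inform the full trial. No analysis plan can recover events that were never asked about.

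**Working it through.** There is no figure in the plan to reproduce, and the point does not depend on a calculation. The check compares what section 8.2 needs with what each stated contact asks.

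**1. What the outcome list needs.** Section 8.2 separates tolerance (item 3) from adverse events (item 8). A question about side effects of the medication suits item 3. Item 8 needs events regardless of cause.

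**2. What the script asks.** Two of the six items ask directly about harms:

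| Item | Subject | Depends on the patient blaming the tablets? |
|---|---|---|
| i | Harms in general | Yes |
| ii | Bleeding | No |
| iii | Adherence | Not a harms question |
| iv | New medication or supplement | Indirect; may reveal an illness |
| v | Concerns about continuing | Indirect; does not ask about health |
| vi | Feedback on medication or trial | Indirect; does not ask about health |

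Bleeding is thus the only harm asked for directly and neutrally.

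**3. What the other contacts ask.**

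- Treatment lasts 12 weeks (section 4.4), and section 10.2 specifies two calls, at weeks 4 and 8.
- The 12-week contact may be a clinic visit or a posted Sydney Swallow Questionnaire (SSQ) (section 10.2).
- From 3 to 12 months the clinic visit is optional. The stated content is return of unused medication and the SSQ, either of which can go by post (section 6.2).
- At 12 months there is a repeat endoscopy with EndoFLIP (section 6.2). No adverse-event question is stated for it.

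For a participant who uses the postal route, the protocol states no contact after week 8, up to the 12-month endoscopy, that asks about harms.

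**4. What the reporting sections add.** Sections 6.7, 6.8 and 6.9 describe how events are reviewed, reported and monitored once known. None says how an event that the patient does not link to the tablets becomes known.

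As written, then, the plan lists adverse events as an outcome but, bleeding apart, actively seeks only those the patient attributes to the medication.

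**The case against.** The strongest reply is that the script is not the only way in. Item iv may bring out an intercurrent illness, items v and vi are open, and notes are taken of anything raised. Clinic visits are available every 3 months, and section 6.4.1 describes a pre-anaesthetic consultation before sedation. Bleeding, the risk singled out in sections 5.2 and 6.4.3, is asked about without the filter. A medication-directed question also fits the stated purpose of the call and the tolerance outcome.

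All of this stands, and it limits the point. These routes are indirect, however; none is a systematic question about health, so the tension with item 8 of section 8.2 remains.

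Several stronger readings are tempting but not supported:

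- **That unattributed events are not collected at all.** The indirect routes above rule this out. Such events are not actively asked for, which is a weaker statement.
- **That an admission not blamed on the tablets can never reach serious adverse event reporting.** Section 6.8 covers all serious events without regard to the patient's opinion, and nothing makes the phone call their sole source. Late or missed detection is possible, but it is not certain.
- **That the patient formally decides causality.** Section 6.7 defers to a guideline that is not at hand, so how relatedness is assigned cannot be judged. The script filters what is volunteered; it does not assign relatedness.
- **That no baseline symptom record exists.** Section 8.2 includes a baseline SSQ, and section 9 mentions case report forms that are not shown.
- **That a numerical loss can be stated.** The protocol gives no attribution fraction. The rates it does give for symptoms of this kind are low: vomiting 1.2%, dry mouth below 1%, and the items quoted from 6.4.2 reported rarely. With 20 patients at a true risk of 1.2%, the chance of recording no case is (1 − 0.012)^20 = 0.79 under full capture. If half were reported (an assumption), it is (1 − 0.006)^20 = 0.89. For any one such symptom an arm of 20 would probably show none under either wording. The effect matters for adverse events taken together and for unanticipated illness or admissions, for which the protocol gives no rate.

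**Conclusion.** The point holds in a limited form. Apart from bleeding, the script asks only for side effects that the patient attributes to the medication, and no other stated contact asks neutrally about adverse events, although these are a listed outcome separate from tolerance. Events put down to radiotherapy, the dilatation or another illness may be under-ascertained.

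The direction is towards absolute adverse-event rates that are too low, in both arms. A reader might infer that the comparison between arms is also biased. The documents do not show this: treatment is double-blind and both arms are asked the same question.

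The size is unknown. The conclusion assumes that follow-up runs as the protocol states and that no document outside it (the case report forms or the cited guideline) adds a neutral question. If one does, the script only needs to be aligned with it. This is a cheap improvement to make before the calls begin, not a flaw that undermines the pilot.

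**What to change.** Replace item i of the script in section 10.2 with a neutral question, for example: *Since the last contact, have you had any new or worsened symptom, illness, injury, doctor visit or hospital admission, whatever the cause?* State in section 6.7 that a blinded investigator assigns relatedness to each event recorded. The bleeding question and the other items can stay as they are.

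Optional additions are the same question at the 12-week and later contacts, or a short symptom checklist. The point does not depend on either.

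The cost is a change of wording in the script and case report form. If the new question adds about 2 minutes per call (an assumption), two calls to each of 40 participants come to 40 × 2 × 2 = 160 minutes over the whole study. The small downside is that more unrelated events will be recorded and need review.
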